| PFIQ-7 | Pelvic Floor Impact Questionnaire |
| QoL | quality of life |
| 2D UL | Two-dimensional Ultrasound |
| 3D UL | Three-dimensional Ultrasound |

[figure not shown]
[figure not shown]
Background:

[figure not shown]
Stress urinary incontinence can significantly diminish the quality of life for many women, limiting their physical activity and impairing sexual function (1). This condition, defined as urinary leakage when coughing, sneezing, or exerting physical effort, has a prevalence of 12-46 % among the general female population (2, 3). For the past two decades, mid-urethral sling (MUS) procedures have been the dominant surgical treatment for SUI and stress-dominant mixed urinary incontinence (MUI). The traditional MUS procedures involve placing a polypropylene mesh under the urethra either in front of the bladder, passing through the pelvis to the lower abdomen (tension-free vaginal tape (TVT))(4), or to the side of the pelvis in the groin area (tension-free vaginal tape obturator inside-out (TVT-O)) (5) (Fig. I). These traditional techniques have well-documented, long-lasting results (6, 7), and have improved the quality of life for many women with SUI (8, 9). MUS procedures have good subjective and objective results for both SUI and stress-dominant MUI and are generally considered safe with low rates of complications (2).

However, in recent years there has been increasing awareness of long-term complications associated with synthetic materials used in these slings, such as chronic pain, dyspareunia, and voiding dysfunction (10). Although these complications are rare, affected women may experience a lifetime of severely reduced quality of life, even if the synthetic material is entirely removed (11). As a result, the health regulatory bodies, hospital administrators, individual surgeons and patients have started to seek out alternative surgical methods.

Single incision mini-slings (SIMS) such as Ajust (Fig. I), which contain much less synthetic mesh than traditional slings, were introduced worldwide in 2006 (12). Later, in 2010, the intermediate sling TVT-O Abbrevio (TVT-A), was introduced hoping to improve the clinical performance of shorter slings (Fig. I) (13). However, there is still a significant knowledge gap regarding short- and long-term results of these new and shorter slings, particularly in terms of complications such as chronic pelvic pain. While some studies have shown promising short-term results for SIMS and intermediate slings, these studies are often small and hampered by selection bias and high rates of lost follow-up (14-22).

FIG.I: The photos depict the traditional slings (TVT and TVT-O), SIMS Ajust and TVT-A.

SIMS Ajust (25)

TTVT-A (26)

[figure not shown]
Given that shorter slings could represent a middle ground between the risk of severe complications and a diminished quality of life (QOL) due to untreated stress urinary incontinence, data on the long-term effects and safety of the newer shorter slings are urgently needed. Retrieving such knowledge would enable the updating of surgical guidelines and provide patients considering surgical options with evidence-based recommendations.

In Norway more than 90% of all female incontinence operations are carried out in public hospitals, and since 2017 the coverage of reporting female incontinence operations has been more than 98 % from public hospitals to the mandatory Norwegian Female Registry (NFIR) (27). This Registry, established in 1998 by The Norwegian Urogynecology Group, is now a compulsory, nationwide quality registry based at Oslo University Hospital (27, 28). Reliable data are collected before surgery, at the time of surgery and at follow-up consultations 6-12-months and 3 years after the surgery. The 6-12 months data has good coverage and will be used in the first part of this PhD project (Part I: REK 22/397503). However, the 3-years reporting has low coverage and are mostly subjective questionnaire-based data. According to the yearly public report from the NFIR, hospitals using the SIMS Ajust and TTVT-A slings seem to have fewer short-term complications than hospitals using the traditional slings (either retropubic or transobturator sling) (29). However, there is still a disagreement about whether the SIMS Ajust and TTVT-A, due to their shorter length, are as effective as the traditional slings. Since its introduction, the TTVT-A has mainly been classified as a TTVT-O sling in the NFIR, and any potential differences in results and complications from regular TTVT-O slings have therefore not been evaluated. Furthermore, there are to date only a few published studies evaluating the effectiveness and complication rates of the SIMS Ajust and TTVT-A (14-22, 30-33). Therefore, it would be of great benefit to surgeons and patients if better scientific data on the short- and long-term effectiveness and complication rates of these slings could be evaluated.

Most of the 39 departments offering female incontinence surgeries in Norway use traditional MUS. However, one of the largest hospitals, Akershus University hospital (AHUS), has been using shorter slings as their preferred MUS since 2009, initially SIMS Ajust and later TTVT-A. At AHUS, we therefore have a unique opportunity to study the long-term results and complication rates of shorter slings by inviting women back for a long-term follow-up after undergoing sling surgery at AHUS. In addition to quality of life, complications, and patient satisfaction, this follow-up provides the possibility of investigating sling position using 2D dynamic and 3D transperineal ultrasound (TPUS) (34-37). This innovative technique that dynamically investigates the pelvic floor and sling placement is not widely used in Norway, but is available at AHUS, which also has expertise in advanced ultrasound within the research group. How the positioning of intermediate slings under the urethra may affect long-term success rates and adverse events is largely unknown. Studies on traditional slings suggest that placement more proximal or distal to the mid-part of the urethra is associated with poorer outcomes (34-36).

Whether this is coincidental or represents an actual association between sling position and long-term success and complication rates is not established for intermediate slings. To go even further, we will evaluate if there is an “optimal sling placement zone”, particularly for shorter slings. This information is currently lacking and makes it difficult for gynaecologists evaluating patients in need of repeat surgery, due to either treatment failure or long-term complications. Understanding the biomechanical effects visualized by ultrasound of the increasingly popular shorter slings would be pioneering work and enable researchers and doctors to further develop the treatment techniques for female incontinence.

Research questions and hypotheses, theoretical approach and methodology

PhD-project, Part 2

Our over-all aim is to evaluate long-term subjective and objective outcomes of shorter slings.

Study design: Prospective observational study

1) Long-term subjective outcomes

Study population: Women treated with SIMS Ajust (n = 744) at Akershus University Hospital between 2009 and 2016 and Intermediate sling TTV-A (n= 318) at Akershus University Hospital between 2016 and 2020.

Follow-up: Potential study participants for both groups will be identified in the local quality database for female incontinence surgery (local NFIR) at AHU S and invited to a long-term follow-up (4-14 years) with questionnaires. The following questionnaires will be sent electronically to the patients together with study invitation and consent form: The validated NFIR questionnaire, the validated Pelvic Floor Impact Questionnaire (PFIQ-7) (38, 39) as well as additional questions regarding pain (40).

- a. *Primary outcomes:* Long-term subjective cure rate.
- Long-term subjective cure is estimated by calculating a stress urinary incontinence index score (SUIS) from 4 clusters of questions measuring degree of symptom bother in the validated NFIR questionnaire, from 0 (no symptoms) to 12 (high symptom load) where a score < 3 is defined as subjective cure (41).
- b. *Secondary outcomes:* Long-term treatment satisfaction scores, quality of life score and complication rates.
- Differences in improvement of quality-of-life using a Quality-of-life index score (QoLIS) generated from 4 questions in the NFIR questionnaire measuring QoL impact. This index ranges from 0 (excellent quality of life) to 16 (poor quality of life) (41). In addition, the Pelvic Floor Impact Questionnaire (PFIQ-7) (38, 39) will be used to further evaluate the Quality-of-life impact.

- Differences in treatment satisfaction rates are defined as the percentage of women answering “very satisfied with treatment” given the options “very satisfied”, “moderately satisfied”, “neither satisfied nor dissatisfied”, “moderately dissatisfied” or “very dissatisfied” in the NFIR questionnaire.
- Differences in total complication rates (all types included), re-operation rates, vaginal tape exposure, persistent and de novo urgency incontinence and prolonged pain.
 - Persistent and de novo urgency incontinence is calculated from the NFIR questionnaire using 4 clusters of questions that generate an urgency urinary incontinence score (UUIS) quantifying the degree of urgency symptom bother from 0 (no symptoms) to 8 (high symptom load) (41). De novo urgency incontinence will be defined as having had a UUIS of ≥ 4 at the long term follow up in women who had no urgency incontinence symptoms before surgery (preoperative urgency urinary incontinence score = 0).
 - Differences in prolonged pain defined as postoperative pain more than 3 months after surgery in the NFIR questionnaire or having had treatment for pain caused by the surgery, e.g removal of the sling or part of the sling. Patients having persistent ongoing pain will further be asked to answer a newly developed non-validated NFIR pain questionnaire (40).

2) Long-term objective outcomes

[figure not shown]
Study population: The 318 women having been treated with the currently most used shorter sling (TVT-A) at Akershus University Hospital between 2016 and 2020 will be invited to a physical follow-up where they will undergo a clinical examination including assessment of objective cure, sling erosions and development of pelvic organ prolapse using the POP-Q system (42).

Exposure: Having had TVT-A sling operation at AHUS.

- a. *Primary outcomes:* Long-term objective cure rates.
- Objective cure will be defined as having no leakage (0 g) at a cough-jump pad weighing stress test (43).
- b. *Secondary outcomes:* The same as defined under 1) Long-term subjective outcomes.
- In addition, we will evaluate differences in the rate of mesh exposures and the development of pelvic organ prolapse (POP) using the POP-Q evaluation system (42).
- The severity of tape exposure will be evaluated using the ICS and IUGA prosthesis and graft complication classification system (44). In addition, we will evaluate the intervention for surgical complications using the Clavien-Dindo Classification (45, 46).

PhD-project, Part 3

We will study the positioning of the shorter sling TVT-A under the urethra using dynamic 2D and 3D ultrasound. We will evaluate if there is an “optimal sling placement zone” for shorter slings.

Our aim is to study the association between sling position, tension and anchoring under the urethra, and subjective and objective cure rate, and long-term complication rates, especially chronic pelvic pain.

Our null hypothesis is that there are no associations between sling position, tension or anchoring of the tape and subjective and objective outcomes including complications such as chronic pain development.

Study design: Prospective observational study

Study population: 318 women having had surgery with the intermediate sling TVT-A at AHUS between 2016 and 2020.

Follow-up: Women who consent to study participation and attend the physical follow-up will undergo a clinical examination that includes a transperineal ultrasound (TPUS) examination in the dorsal lithotomy position using a 3,5-6 MHz curved array abdominal probe (47). The TPUS volumes and images will be obtained with an empty bladder at rest and under full Valsalva (48).

Exposure: Position, tension (shape) and anchoring of the sling, and measuring sling position in relation to well-defined anatomical markers.

- a. *Primary outcomes:* Any association between sling position, tension or anchoring and subjective and objective cure rate, complication rates and especially the development of chronic pelvic pain. For the definitions of cure rates, *see under part 2*.
- b. *Secondary outcomes:* Any association between sling position, tension or anchoring and long-term complications, especially chronic pelvic pain, *see part 2*.

Statistics, power and sample size:

PhD-project, Part 2

This is a follow-up study of all women having been operated at AHUS with SIMS Ajust or TTVT-A in the study period. Few studies with long-term outcomes after shorter slings have been published. The first part of the long-term follow-up will therefore be a prospective follow-up study with no group comparisons. For this part, power calculations are not feasible as all women having had SIMS Ajust or TTVT-A in the study period consenting to study participation will be analysed for subjective outcomes, whereas all women in the TTVT-A group consenting to study participation will be analysed for objective outcomes.

PhD-project, Part 3

For the transperineal ultrasound (TPUS) part of the project, various outcomes will be evaluated based on sub urethral sling position, tension and anchoring. As there is little scientific published data on how sling placement affect subjective and objective outcomes of sling surgeries, a pre-study sample size estimation must in part be made on best clinical guess. Based on the following assumptions:

We estimate that 80 % of the women will have the sling placed in the “optimal position” and 20 % outside the optimal position as shown in a small study published in 2017 by Hegde and co-workers (37). Therefore, the estimated group ratio will be 1:4.

A clinically relevant effect size (group difference) regarding subjective outcomes is not established, but based on our clinical experience, we have set the minimal relevant group difference in success rate to 30 % (85 % subjectively cured in the “optimal position” group vs 55 % in the “non-optimal position group”).

With a significance level (α) of 0,05 and a statistical power (β) of 80%, the estimated sample size to be included for TPUS evaluation is 107 women (37). Even though we invite all 318 TTVT-A women to attend the physical long-term follow-up with ultrasound evaluation, realistically we estimate that only 50 % will want to participate. Even with 50 % participation we should, based on our sample size calculation, be able to draw valid conclusions.

Risk evaluation and countermeasures

The main risk to the project is patient inclusion. To get robust and valid scientific data we are depending on women being willing to participate in the project with clinical examinations and ultrasound measurements. Based on previous experience, Norwegian women usually do want to participate in long-term follow-up studies. In the 10-year follow-up study of retropubic TVTs conducted by the main supervisor [name] 89 % consented to study participation, and 60 % to a physical follow-up (6). Even a conservative estimate of 50 % would therefore be enough to draw valid conclusions. However, if less than 50 % agree to study participation, we do have the possibility to extend the study period to include women operated in 2021. According to the work plan for the PhD project (below) these women will then be evaluated in 2024 at the earliest and as such have follow-up of minimum 4 years.

User Participation

The project has two user representatives, [name] as part of NFIRs national Advisory Unit and [name] as user representative at the Women's Clinic, AHUS. They have both participated in the planning of the project and given valuable comments in developing the study protocol. Both have agreed to stay on as part of the project group. We plan on having quarterly meetings with the user representatives throughout the whole project period.

Ethical considerations

The Department Head at AHUS has already approved the study. Furthermore, the study will be sought approved by NFIR Management team, NFIRs professional council, The Data Protection Officer at AHUS as well as the Regional Committee for Medical and Health Research Ethics in the Southeast of Norway (REC South East). Signed consent will be obtained from all study participants.

Study participants will only be examined using established techniques for the evaluation of women after incontinence surgery, the exception being the 3D ultrasound examination. None of them involves any additional risk for the participants.

Questionnaires and consent forms will be sent electronically and stored at the Services for Sensitive Data (TSD), as well as the research server at AHUS. Study participants who report persistent or recurring incontinence as well as any long-term complications related to the slings will be offered a full new clinical evaluation.

Potential impact of the proposed research

The proposed research has the potential to significantly impact the surgical management and treatment of women with urinary incontinence, both nationally and abroad. This study aims to address critical knowledge gaps that, when filled, could improve the quality of life for women with this condition. The study's pioneering approach of establishing an "optimal placement zone" for slings may prove to be an innovative tool in decision-making after failed surgery and in women experiencing severe long-term complications, such as chronic pelvic pain. Providing women with evidence-based data on short- and long-term success rates of shorter slings and the incidence of long-term risks for severe complications, such as chronic pain, is highly sought after in the ongoing controversy surrounding the use of synthetic implants vaginally.

Publication of results

The results from the PhD project will be published as three Papers in internationally peer-reviewed journals. Furthermore, the study's findings will be presented at the Annual Meeting of The Norwegian Society for Gynecology and Obstetrics, and at the Yearly NFIR meeting, and at international Urogynecology conferences such as the Annual Meeting of the International Continence Society. This is crucial in ensuring

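### Cure is defined only by status at long-term follow-up, so a woman who is continent after a repeat stress-incontinence procedure counts as a cure of the index sling

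*Protocol*

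**What the plan says.** **Subjective cure.** In Part 2, under Long-term subjective outcomes, the primary outcome comes from a stress-incontinence index scored 0 to 12 on a questionnaire sent 4 to 14 years after surgery, "where a score < 3 is defined as subjective cure".

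**Objective cure.** Under Long-term objective outcomes, for the TVT-A women only: "Objective cure will be defined as having no leakage (0 g) at a cough-jump pad weighing stress test".

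**Who is analysed.** The Statistics section for Part 2 takes every consenting woman with either sling for the subjective analysis: "all women having had SIMS Ajust or TTVT-A in the study period consenting to study participation will be analysed for subjective outcomes". The objective analysis is limited to one sling but is otherwise just as inclusive: "whereas all women in the TTVT-A group consenting to study participation will be analysed for objective outcomes". No separate handling is given for women treated again.

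**Re-operation.** It appears among the secondary outcomes: "Differences in total complication rates (all types included), re-operation rates, vaginal tape exposure". It is not restricted to procedures for stress incontinence and is not linked to cure.

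**What the result is said to show.** The Background wants "better scientific data on the short- and long-term effectiveness and complication rates of these slings could be evaluated". Part 2 opens with "Our over-all aim is to evaluate long-term subjective and objective outcomes of shorter slings". The section on potential impact promises "evidence-based data on short- and long-term success rates of shorter slings".

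**Part 3.** It studies the position, tension and anchoring of the TVT-A and takes its cure definitions from Part 2.

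**The concern.** The cure rule records whether a woman is continent at follow-up, while the stated aim is how well the sling performed. The two differ for any woman whose index sling failed and who was then operated on again for stress incontinence. If the second procedure worked, the rule records a success, although the repeat operation is evidence that the first sling failed.

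Part 2 makes no group comparison, so the error cannot cancel against a control group, and a higher response rate does not shrink it. In Part 3, a cure produced by a second procedure could be related to the position of the first tape.

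This goes beyond detail that a protocol may leave for later. The protocol defines both primary outcomes completely, and in other outcomes it writes a woman's history into the definition. Prolonged pain includes women already treated for pain caused by the surgery, for example by removing the sling. De novo urgency depends on the preoperative score. Cure has no such clause, so pain that was treated still counts as a complication, while a failure that was treated can count as a success.

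**Working it through.** **The plan's own figure.** Part 2 has no calculation. The only one in the protocol is the 107 women for Part 3, which uses the same subjective cure. The arcsine formula with 85% against 55%, a 1:4 ratio, two-sided 0.05 (sidedness assumed) and 80% power gives 21.5 x 5 = 107.6, which agrees with 107. The present point does not depend on that figure.

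**Formula.** Let C be meeting the cure rule at follow-up and R having had a repeat stress-incontinence procedure since the index operation. The plan's rate is P(C). If a repeat procedure is taken as failure of the index sling, the index-sling rate is P(C and not R). The difference is

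P(C and R) = P(R) x P(C given R).

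**Inputs.** The documents give neither factor. Assumed ranges are P(R) = 2-10% and P(C given R) = 50-85%.

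**Overstatement of subjective cure, in percentage points:**

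| Re-operated | 50% meet rule | 75% meet rule | 85% meet rule |
|---|---|---|---|
| 2% | 1.0 | 1.5 | 1.7 |
| 5% | 2.5 | 3.75 | 4.25 |
| 10% | 5.0 | 7.5 | 8.5 |

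**In women.** The cohort is 744 + 318 = 1,062. The protocol's cautious 50% participation is stated for the physical follow-up; applied here as an illustration, it gives 531 women. Then 531 x 0.010 = 5.3 and 531 x 0.085 = 45.1, so about 5 to 45 women.

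**Against sampling error.** A reference cure rate is needed. Weighting the Part 3 planning values gives 0.2 x 0.55 + 0.8 x 0.85 = 0.79. Those values are guesses for TVT-A position groups, so using 79% for both slings together is an assumption. The 95% half-width is 1.96 x sqrt(0.79 x 0.21 / n):

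- n = 531: 3.5 points
- n = 945 (0.89 x 1,062, using the consent rate of the earlier retropubic follow-up cited under Risk evaluation): 2.6 points

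With 75% of re-operated women meeting the rule, the overstatement exceeds the half-width once the re-operated share passes 3.46 / 0.75 = 4.6% (n = 531) or 2.60 / 0.75 = 3.5% (n = 945).

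**Objective cure and Part 3.** The same identity applies, but no figure is given. The TVT-A women were operated between 2016 and 2020, later than the Ajust women, so they have had less time for repeat surgery. The documents give no expected objective cure rate, and no re-operation rate by sling position.

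**The case against.** **The protocol does not say outright that re-treated women count as cured.** True. It follows from unconditional rules applied to all consenting women. The sentence about who is analysed explains why no power calculation was made and was not written as a rule for repeat surgery. A later analysis plan could add one. Even so, the primary outcomes are complete as written, and following them gives this result.

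**Continence at follow-up, whatever happened in between, is a legitimate quantity.** This stands. It describes how women fare after starting with a shorter sling. The difficulty is the label: the protocol presents the figure as the effectiveness and success rate of the slings.

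**The overlap could be tabulated.** Also true. A reader might infer that the index-sling rate will be unrecoverable. The documents do not support that, because cure and re-operation are both planned outcomes in the same women and nothing says that their cross-tabulation will be withheld. It is simply not planned, and the re-operation rate does not isolate stress-incontinence procedures.

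**The size is assumed.** Yes, entirely. At the low end it is well inside sampling error.

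**Part 3.** A reader might infer that Part 3 loses power or that its association is distorted by a known amount. Without re-operation rates by sling position, the documents support neither statement.

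**Conclusion.** The point holds in limited form. As written, the cure definitions credit the index sling with continence achieved by a later stress-incontinence procedure, and the protocol presents the result as the success of the sling.

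For subjective cure the overstatement is 1.0 to 8.5 points if 2-10% were re-operated for stress incontinence and 50-85% of them then meet the rule. It may be negligible or may exceed the sampling error; which of these applies cannot be told from the documents. For objective cure it is probably smaller. For Part 3 the mismatch is one of definition only, with no size attached.

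A reader might infer that the reported cure rate is certain to be materially too high. That does not follow: the bias is zero if no re-operated woman meets the rule. The definition should be corrected before outcomes are seen, because a choice made afterwards could look selected for its effect on the headline rate.

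**What to change.** 1. Define the primary index-sling cure as a stress-incontinence index below 3 (objective: 0 g) and no repeat procedure for stress incontinence since the index operation. Use this in Parts 2 and 3.
2. Report the status-only rates as supportive, labelled as continence at follow-up regardless of further treatment, with a cross-tabulation of cure by repeat procedure.
3. Record the occurrence of and reason for each re-operation, so that stress-incontinence procedures can be separated from others.
4. In Part 3, keep re-operated women as index failures wherever the index TVT-A can be measured, and report the number and outcomes of the rest. Excluding women because they have a second sling would remove index failures.

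**Cost.** The wording is one clause in each definition, and the headline cure rate will be somewhat lower. The real work is ascertainment: re-operations and their reasons must be obtained from patient report, hospital records and the registry over a period of up to 14 years. The Background states registry coverage above 98% only since 2017 and only for public hospitals, whereas the Ajust operations ran from 2009 to 2016. Some repeat procedures may be missed, so some overstatement may remain. In Part 3 the examiner must also note which tape is the index TVT-A when two are visible.

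### Subjective cure is judged on the follow-up score alone in all consenting women, so a woman already below the cut-off before surgery can count as cured

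*Protocol*

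**What the plan says.** In the protocol, PhD-project Part 2, under 1) Long-term subjective outcomes, the primary outcome is built from the NFIR questionnaire at follow-up, "where a score < 3 is defined as subjective cure". The definition has no preoperative condition.

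The population is set by device, hospital and years of surgery: "Women treated with SIMS Ajust (n = 744) at Akershus University Hospital between 2009 and 2016", plus 318 women with the TVT-A sling from 2016 to 2020. No baseline score enters. Under Statistics, power and sample size, "all women having had SIMS Ajust or TTVT-A in the study period consenting to study participation will be analysed for subjective outcomes". Part 3 refers back to Part 2 for its cure definitions.

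One secondary outcome in the same section does look at baseline. De novo urgency is assessed only "in women who had no urgency incontinence symptoms before surgery (preoperative urgency urinary incontinence score = 0"). The Background says of the registry that "Reliable data are collected before surgery, at the time of surgery and at follow-up consultations".

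**The concern.** Cure means that a condition was present and is now gone. The protocol's rule records only the second half. By the study's own threshold, a woman operated on with a preoperative SUIS of 0 to 2 had no stress incontinence to be cured of, yet she enters the numerator if she is unchanged.

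Two results are exposed. The first is the Part 2 subjective cure rate, which is meant to inform women and surgeons about how well shorter slings work. Its value would depend partly on how many low-scoring women were operated on. The second is the Part 3 association of sling position with subjective cure, where such women add successes that position cannot explain and so narrow the contrast.

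This is not a detail left to a later analysis plan, because the protocol itself fixes the definition, the population and the analysis set.

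**Working it through.** **Can the case arise on the text?** The definition uses the follow-up score only, the population has no baseline criterion, and all consenting women are analysed. Nothing removes a woman with a preoperative SUIS below 3.

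**Shift in the Part 2 rate.** Let f be the share of women below the cut-off before surgery, r the share of those who are below it at follow-up, and c the cure rate among the rest. The reported rate is (1 − f) × c + f × r, so the shift is f × (r − c).

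The documents give neither f nor r; f = 3–10 % and r = 95 % are assumptions. For c the only planning rates are 85 % and 55 %, in an expected 4:1 split (Statistics, power and sample size), which averages 0.8 × 85 + 0.2 × 55 = 79 %. I take c = 70–85 %.

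| f | c | f × (0.95 − c) | Shift, points |
|---|---|---|---|
| 3 % | 85 % | 0.03 × 0.10 | +0.3 |
| 3 % | 70 % | 0.03 × 0.25 | +0.75 |
| 10 % | 85 % | 0.10 × 0.10 | +1.0 |
| 10 % | 70 % | 0.10 × 0.25 | +2.5 |

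The sign depends on r. At r = c the shift is zero. At r = 70 %, c = 80 % and f = 10 % it is 0.10 × (0.70 − 0.80) = −1.0 point.

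**Part 3: the plan's own figure.** The protocol states 107 women for 85 % against 55 %, ratio 1:4, alpha 0.05 (taken as two-sided) and 80 % power. The arcsine formula gives h = 2 × (asin √0.85 − asin √0.55) = 0.675. The smaller group is then (1.960 + 0.842)² × 1.25 / 0.675² = 21.5, and the total is 5 × 21.5 = 107.6. The stated figure is reproduced.

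**Part 3: effect of low-baseline women.** If f and r are equal in both position groups, the contrast becomes (1 − f) × 30 points: 29.1 at f = 3 % and 27.0 at f = 10 %. Power is Φ(h × √(0.16 × N) − 1.96), with h recalculated from the diluted rates (r = 1). The expected attendance is 50 % of 318 = 159.

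| f | Contrast, points | Power at 107 | Power at 159 |
|---|---|---|---|
| 0 % | 30.0 | 79.8 % | 92.6 % |
| 5 % | 28.5 | 76.9 % | 90.7 % |
| 10 % | 27.0 | 73.7 % | 88.6 % |
| 20 % | 24.0 | 66.9 % | 83.2 % |

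**Room for restriction.** At f = 10 %, 159 attendees leave 159 × 0.9 = 143 women, still above 107. Up to 159 − 107 = 52 attendees, about a third, could be set aside for a low or missing baseline score before the restricted set falls below the stated size.

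**The case against.** The affected group may be very small. Everyone in the cohort had a sling operation, and the Background gives the indication for these procedures as stress or stress-dominant mixed incontinence. No passage reports a woman with a low preoperative SUIS. This stands, and it is why the size is given only as a range on stated assumptions.

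A reader might infer that the cure rate is certainly inflated. The documents do not support that. The shift is upward only if r exceeds c, and nothing in them shows that low-scoring women stay low over 4 to 14 years.

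A reader might also carry the point over to objective cure, since "Objective cure will be defined as having no leakage (0 g) at a cough-jump pad weighing stress test" has no baseline condition either and "all women in the TTVT-A group consenting to study participation will be analysed for objective outcomes". The wording is parallel, but the remedy does not carry over. The documents do not say that a preoperative pad test is held, and a single 0 g result would not show that stress incontinence was absent.

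Nor is the de novo urgency rule a contradiction. De novo requires absence at baseline by its meaning, whereas a cure definition based on follow-up state is a possible convention. The rule matters only because it shows that preoperative scores from the same questionnaire are to be used.

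Finally, no conclusion hangs on the shift. Part 2 compares no groups and sets no success threshold. At a rate of 80 %, the 95 % half-width with 531 responders (assuming 50 % of 744 + 318 = 1062) is 1.96 × √(0.8 × 0.2 / 531) = 3.4 points, more than the largest shift in the range. That limits the importance of the point but does not remove it: a larger sample would not correct a definitional shift, and the label would still be inaccurate.

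**Conclusion.** The point holds for subjective cure, as a minor one. As written, the primary outcome is the share of women with SUIS below 3 at follow-up, and it is reported as cure. With 3–10 % of women below the cut-off before surgery, 95 % of them still below it and 70–85 % cure in the rest, the rate is about 0.3 to 2.5 points too high. It is unchanged or too low if r is no greater than c. The share f is not in the documents and has to be counted from the registry.

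One might conclude that Part 3 is left underpowered. The figures do not bear that out: at the expected 159 attendees power stays at 88.6 % with f = 10 %, and at 83.2 % with f = 20 %. It would fall below 80 % only if attendance came down towards the stated minimum of 107.

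**What to change.** Define subjective cure as follow-up SUIS < 3 among women with a recorded preoperative SUIS of 3 or more. Report beside it the rate in all consenting women, labelled as continent (SUIS < 3) at follow-up. State how many women had a preoperative SUIS below 3 and how many have no baseline score. Repeat the Part 3 association with subjective cure in the restricted set. Leave the objective cure definition as it is.

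The work is one filter. The de novo urgency rule already needs a preoperative score from the NFIR questionnaire, which also yields the SUIS. The cost is a slightly smaller denominator and some loss to missing baseline scores. That loss could matter for the Ajust women: the registry coverage above 98 % in the Background applies from 2017, after their operations in 2009 to 2016, so the completeness of their baseline scores is not documented. Giving both rates with the counts lets the reader judge whether the restriction has introduced selection of its own.
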